6.1.4 Discontinuation of Therapy

The Investigator will withdraw a patient whenever continued participation is no longer in the patient's best interests. Reasons for withdrawing a patient include, but are not limited to, disease progression, the occurrence of an adverse event or a concurrent illness, a patient's request to end participation, a patient's non-compliance or simply significant uncertainty on the part of the Investigator that continued participation is prudent. There may also be administrative reasons to terminate participation, such as concern about a patient's compliance with the prescribed treatment regimen

Table 6.1: Schedule of Study Procedures and Assessments⁴

	Screen	Days Pre-HSCT			Days Post-HSCT				Weeks Post-HSCT					TMA Dx
(+/- in days)	Admit (-28)	Admit	-7 (+/- 2)	-1 (+/- 1)	7 (+/- 2)	14 (+/- 2)	21 (+/- 2)	28 (+/- 2)	8 (+/- 7)	12 (+/- 7)	16 (+/- 7)	20 (+/- 7)	24 (+/- 7)	Dx (+/- 3)
Informed consent	X													
AE assessment		X	X	X	X	X	X	X	X	X	X	X	X	X
Defibrotide		X	X	X	X	X	X							+/-
Physical exam *		X	X	X	X	X	X	X	X	X	X	X	X	X
Vital signs *		X	X	X	X	X	X	X	X	X	X	X	X	X
Medical History *		X	X	X	X	X	X	X	X	X	X	X	X	X
Standard Labs ¹ *		X	X	X	X	X	X	X	X	X	X	X	X	X
Study Labs ²		X³		X	X		X							X

1. Labs per standard of care should include CBC, complete chemistry, LDH, uric acid, haptoglobin, direct antiglobulin test, peripheral smear for RBC morphology, urine protein concentration, urine protein / creatinine ratio, CH50, coagulation panel.
 2. Study labs to include plasma free Hgb, ST2, Ang-2, PAI-1, and hold specimen.
 3. +/- 2 day window
 4. Patients undergoing tandem autologous transplants will repeat the schedule of procedures and assessments on admission for second transplant, with the exception of screening.
- * Standard of care for patients undergoing HSCT

6.2 Usage of Concurrent/Concomitant Medications

Patients on the trial will receive the UCSF standard of care for high risk TMA

- Vitamin D started prior to admission with goal levels of vitamin D, 25 hydroxy level of 30- 60ng/mL
- Allopurinol on admission and continue until Day 0 if uric acids are normal, or longer if uric acids remain high
- Two weeks prior to admission patients will begin Eicosapentaenoic Acid (EPA, a component of fish oil). (dosing: < 6 months: 110 mg PO qday, 6 months – 17 years: 30 mg/kg/day, max 2000 mg/day) divided up to three times per day) which will continue until day +100. EPA will be held when patient is unable to take PO, during periods when the patient's platelet count is < 20 x 10⁹/L, for clinical bleeding, prior to procedures (hold at least 4 days prior to procedure), and/or requiring platelets transfusions. Clinical trial evidence for EPA does not support an increased bleeding risk with fish oil therapy, even when used in combination with other agents that may increase bleeding.
- n-Acetylcysteine (NAC) prophylaxis in addition to those doses given on admission, and Day +1 and Day +2 for VOD prophylaxis will be given as 70 mg/kg (rounded to nearest vial size) every 8 hours IV or PO starting day +3 and continued until Day +42 or discharge, whichever comes sooner.

There are no restrictions in concurrent / concomitant medications except per standard of care recommendations for use of defibrotide. Specifically, tissue plasminogen activator (t-PA) is contraindicated due to bleeding risk; use of low doses for clearance of IV catheters is permitted. Administration of other anticoagulants concurrently with defibrotide is at the discretion of the treating physician.

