3.3.2 Exclusion Criteria

1. Age >30 years
2. Life expectancy < 6 months
3. Known bleeding diathesis or bleeding risk deemed by the treating physician to be a contraindication to administration of anticoagulants.
4. Known hypersensitivity reaction to defibrotide
5. Any patient not meeting TMA High-Risk criteria as defined in section 1.3
6. Pregnant women are excluded from this study because they will be receiving teratogenic therapy as part of the stem cell transplant.

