4.1 Description, Supply and Storage of Investigational Drugs

4.1.1 Investigational Drug #1

Defibrotide is available as a solution, Intravenous, as sodium [preservative free]: Defitelio: 200 mg/2.5 mL (2.5 mL). Refer to the package insert for complete information.

Classification:

Therapeutic Category: Antiplatelet Agent; Thrombolytic Agent

Mechanism of Action:

Defibrotide augments plasmin enzymatic activity to hydrolyze fibrin clots. It reduces endothelial cell (EC) activation and increases EC-mediated fibrinolysis by increasing tissue plasminogen activator and thrombomodulin expression, as well as by decreasing von Willebrand factor and plasminogen activator inhibitor-1 expression.

Metabolism:

Polynucleotides are metabolized via nucleases, nucleotidases, nucleosidases, deaminases, and phosphorylases to oligonucleotides, nucleotides, nucleosides, and then to the free 2'-deoxyribose sugar, purine and pyrimidine bases

Contraindications:

Known hypersensitivity to defibrotide or any component of the formulation; concomitant administration with systemic anticoagulant or fibrinolytic therapy

Availability:

FDA approved March 2016

Storage and handling

Store intact vials at 20°C to 25°C (68°F to 77°F); excursions permitted between 15°C to 30°C (59°F to 86°F). Solutions diluted for infusion in D5W or NS should be used within 4 hours if stored at room temperature or within 24 hours if refrigerated. Discard partially used vials. Side

Effects

Complete and updated adverse event information is available in the Investigational Drug Brochure and/or product package insert.

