5.1.1 Dose Modifications and Dosing Delays Tables for Specific Adverse Events

Adverse Event: Bleeding or Hypersensitivity reaction

Grade of Event	Management
≤ Grade 1	No change in dose
Grade 2	Hold until ≤ Grade 1 Resume at same dose level
Grade 3	Discontinue therapy
Grade 4	Discontinue therapy

*Patients requiring a delay of > 2 weeks should go off protocol therapy

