6.4 Prohibited Medications

Eculizumab if used as prophylaxis for TMA, Ibuprofen or other NSAIDs, aspirin

7 Reporting and Documentation of Results

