Appendix 2 Prohibited Medications

Drug	Trade name (if applicable)
aspirin	
alteplase (systemic)	Activase
eculizumab (prophylactic)	Soliris
ibuprofen	Advil, Motrin
naproxen	Aleve

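### Section 6.2 leaves anticoagulants given with defibrotide to the treating physician, although 4.1.1 contraindicates systemic anticoagulant therapy with it, and neither prohibited-drug list names one

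*Combined protocol and SAP*

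**What the plan says.** Four places in the combined protocol and SAP bear directly on the question.

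- **4.1.1 (Contraindications).** Besides known hypersensitivity, it lists "concomitant administration with systemic anticoagulant or fibrinolytic therapy". No dose, route or clinical exception is given.
- **6.2 (Concomitant medications).** The general rule is "There are no restrictions in concurrent / concomitant medications except per standard of care recommendations for use of defibrotide". The section then takes up t-PA. It is contraindicated because of bleeding, with one carve-out: "use of low doses for clearance of IV catheters is permitted". The next sentence reads "Administration of other anticoagulants concurrently with defibrotide is at the discretion of the treating physician".
- **6.4 (Prohibited medications).** The whole entry is "Eculizumab if used as prophylaxis for TMA, Ibuprofen or other NSAIDs, aspirin".
- **Appendix 2.** It lists aspirin, systemic alteplase, prophylactic eculizumab, ibuprofen and naproxen. No anticoagulant appears.

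Two other provisions come close. Exclusion 3 in 3.3.2 keeps out patients with a known bleeding diathesis or a "bleeding risk deemed by the treating physician to be a contraindication to administration of anticoagulants". The dose-modification table in 5.1.1 is headed "Adverse Event: Bleeding or Hypersensitivity reaction". It holds drug at Grade 2, discontinues at Grade 3 or 4, and takes patients off protocol therapy when a delay exceeds two weeks.

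**The concern.** A treating physician who wants to know whether a patient on defibrotide may receive a systemic anticoagulant will look in 6.2, 6.4 and Appendix 2. The first leaves it to judgment and the other two are silent. Only the drug description in 4.1.1 says the combination is contraindicated.

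Two things are at stake. The first is patient safety: 1.3 describes defibrotide as itself anticoagulant and fibrinolytic, and 5.2 warns that it may raise bleeding risk. The second is the reading of a primary endpoint. Section 2.4.1 counts bleeding serious enough to stop therapy. With no control arm, a bleed on defibrotide plus an anticoagulant cannot be separated from a bleed on defibrotide alone, except by case-by-case attribution. The schedule in Table 6.1 and the visit lists in 6.1.2 and 6.1.3 have no concomitant-medication item, although the medical history row might pick up such exposure.

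**Working it through.** The plan states no figure on this point, so the check is a comparison of texts.

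**Step 1: does each half of the contraindication in 4.1.1 reach the operating rules?**

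| Part of 4.1.1 | 6.2 | 6.4 | Appendix 2 |
|---|---|---|---|
| Systemic fibrinolytic | t-PA contraindicated; low-dose line clearance allowed | not listed | systemic alteplase listed |
| Systemic anticoagulant | physician's discretion | not listed | not listed |

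The fibrinolytic half was carried over for t-PA. The anticoagulant half was not.

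**Step 2: is the discretion bounded elsewhere in 6.2?** The clause deferring to standard-of-care recommendations for defibrotide could bring in the contraindication. But the text goes on to spell that clause out for t-PA only, and the following sentence gives anticoagulants a different treatment. The authors wrote a catheter limit for t-PA and none for anticoagulants. The same section gives fish oil explicit hold rules (platelets below 20 x 10⁹/L, clinical bleeding, procedures) while saying that trial evidence does not support an increased bleeding risk with it. Anticoagulants have no limit of agent, dose, route or platelet count.

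**Step 3: does another provision decide the matter?**

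- Exclusion 3 screens for bleeding risk at entry. It says nothing about an anticoagulant started later.
- Section 5.1.1 acts once bleeding or hypersensitivity has occurred.
- Section 5.2 bars starting defibrotide during active bleeding.
- Sections 3.4 and 6.1.4 let the investigator end treatment for intercurrent illness or on judgment. They allow a stop but do not require one, and they do not forbid the combination.
- Weekly PT/PTT (6.1.2), attribution (7.5), monthly committee review (7.7) and analysis of reasons for stopping (8.4.2) detect or describe consequences.

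None says whether the combination is allowed.

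**Step 4: can the harm be sized?** That would need the share of patients who would receive a systemic anticoagulant and the bleeding rates with and without one. The documents give none of these, so no estimate is offered.

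**The case against.** The best case for the plan is that its sentences can be read together. Section 4.1.1 stays in force, 6.2 opens by deferring to standard-of-care recommendations for defibrotide, and the discretion sentence does not use the word systemic. On that reading, discretion covers only what the contraindication leaves open, such as line flushes. Sections 3.4 and 6.1.4 also give the investigator a route to stop defibrotide when anticoagulation is needed.

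This reading is possible, but it asks the physician to supply a limit that 6.2 states for t-PA and omits for anticoagulants. A safety instruction should not depend on that. The stopping routes narrow the gap in practice without closing it.

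Three parts of the opposing case stand:

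- A reader might infer that 4.1.1 bars every anticoagulant dose, prophylactic included. It speaks of systemic therapy, and nothing in the documents settles whether prophylactic dosing falls within it.
- A reader might infer that needing an anticoagulant must end defibrotide for good. Section 4.1.1 concerns concomitant use, so a hold would honour it, and 5.1.1 already tolerates delays of up to two weeks.
- A reader might infer that the trial leaves bleeding unmanaged. The entry exclusion, hold and stop rules, coagulation panels and committee review are real safeguards. What is missing is a rule on the combination itself.

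**Conclusion.** The concern holds as an internal contradiction in a safety instruction: 6.2 as written permits a combination that 4.1.1 contraindicates, and the two prohibited-drug lists do not resolve it. It should be fixed. Confidence is high on the wording mismatch. It does not extend to consequences: the documents do not support any claim that bleeding will be more frequent by a given amount, or that many patients will be exposed.

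The conclusion assumes that a physician would follow the specific sentence in 6.2 over the general clause before it, and that no deliberate departure from 4.1.1 was intended, since none is acknowledged or justified. The point does not affect the plan's power calculations or its suspension thresholds. It would be wrong, however, to say that enrolment is certainly unaffected, because that turns on 8.2.2.

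**What to change.** **Wording**

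1. In 6.2, replace the discretion sentence with a bar on systemic anticoagulant therapy while defibrotide is being given. Keep discretion only for low-dose use to maintain catheter patency, parallel to t-PA.
2. Add systemic anticoagulants to 6.4 and Appendix 2.
3. State that defibrotide is held while systemic anticoagulation is needed and stopped if the delay exceeds two weeks. The two-week limit in 5.1.1 now sits under the bleeding and hypersensitivity table, so its extension to this case must be written down.
4. State that such a patient counts in the missed-dose or discontinuation tally, and say whether 8.2.2 replaces the patient. That section replaces those who discontinue participation for reasons other than direct toxicity or failed feasibility. A stop for anticoagulation could be classed either way, and a patient off drug but still followed may not have discontinued participation at all.

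If discretion is intended, 4.1.1 and 6.2 should instead acknowledge the departure and its conditions, and each bleeding event should be listed with any concurrent anticoagulant.

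**Cost** (these figures measure the fix, not the harm avoided)

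- *Holds.* At one dose every 6 hours there are 24/6 = 4 doses a day. A full 14-day hold misses 14 x 4 = 56 doses. The Abstract's 28 to 35 days is 112 to 140 doses, so such a hold costs 56/140 = 40% to 56/112 = 50% of a course.
- *Stops.* Each adds 1/24 = 4.2 percentage points to the discontinuation proportion with the 24 patients in section 8, or 1/25 = 4.0 with the 25 in the Abstract and 3.2. Reaching the last trigger in 8.1 (12 patients at 19 to 24 accrued) through such stops alone would take 12/24 = 50% of the cohort.
- *Enrolment.* Patients who received defibrotide stay in the 8.4.1 analysis population. If 8.2.2 is read to replace them, each adds one to enrolment.

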6.3 Dietary Restrictions

None

6.4 Prohibited Medications

Eculizumab if used as prophylaxis for TMA, Ibuprofen or other NSAIDs, aspirin

7 Reporting and Documentation of Results

7.1 Evaluation of Efficacy (or Activity)

Incidence of TMA will be calculated on a rolling basis and at completion of the study. If at any time incidence of TMA exceeds 2 patients, the study will be paused and evaluated for futility.

7.2 Definitions

7.2.1 Definition of TMA

Criteria for diagnosis of TMA for purposes of this study will be as follows:

- Evidence of microangiopathy, with an additional item from Category A or B, OR
 - The presence of schistocytes (>2/HPF) in the peripheral blood, or
 - Histologic evidence of microangiopathy on a tissue specimen, or

- Undetectable haptoglobin with increased reticulocyte count
- No evidence of microangiopathy but:
 - 1 item from Category A (evidence of organ dysfunction), AND
 - 3 items from Category B (increased TMA biomarkers)

Category A (clinical markers / organ dysfunction)	Category B (biomarkers)

 • Proteinuria • Hypertension • Renal dysfunction 	
 • De novo anemia • Do novo thrombocytopenia • Elevated LDH • Terminal Complement Activation

*Definitions of these criteria are provided below.

Definitions of criteria are adapted from Jodele et al (2015 Blood Rev) and provided below:

Laboratory or clinical marker	Description
1. Lactate dehydrogenase (LDH)	
 • Elevated above the upper limit of normal for age
2. Proteinuria	
 • A random urinalysis protein concentration of ≥ 30 mg/dL or abnormal Pr/Cr Ratio
3. Hypertension	
 • <18 years of age: a blood pressure at the 95th percentile value for age, sex and height. • ≥ 18 years of age: a blood pressure $\geq 140/90$ mm Hg.
4. De novo thrombocytopenia	
 • Thrombocytopenia with a platelet count $< 50 \times 10^9/L$ or a $\geq 50\%$ decrease in the platelet count
5. De novo anemia	
 • A hemoglobin below the lower limit of normal for age anemia requiring transfusion support
6. Evidence of microangiopathy	
 • The presence of schistocytes ($>2/HPF$) in the peripheral blood, or • histologic evidence of microangiopathy on a tissue specimen, or • Undetectable haptoglobin with increased reticulocyte count
7. Terminal complement activation	
 • Elevated plasma concentration of sC5b-9 above upper normal laboratory limit
8. Renal dysfunction	
 • Elevated creatinine above upper limit of normal not due to alternative cause (e.g., drug, fluid status)

7.2.2 Definition of Severe TMA

Any TMA meeting criteria described in 7.2.1 with any of the following additional features:
• Renal dysfunction requiring dialysis
• Pleural or pericardial effusion requiring any medical or surgical intervention
• CNS dysfunction including seizure
• Inpatient admission > 90 days duration directly related to TMA management

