5. I agree to maintain adequate and accurate records in accordance with CHR policies, Federal, state and local laws and regulations.

UCSF Principal Investigator / Study Chair

Printed Name

Signature

Date

Participating Site(s)

Telephone:
E-mail:

Telephone:
E-mail:

Telephone:
E-mail:

Principal Investigator

Site

Printed Name

Signature

Date

Abstract

Title	A Pilot Trial of Using Pre-Transplant Risk Stratification and Prophylactic Defibrotide to Prevent Serious Thrombotic Microangiopathy in High-Risk Hematopoietic Stem Cell Transplant Patients
Patient population	Pediatric patients age 0-30 years receiving autologous or allogeneic HSCT meeting TMA high risk criteria.
Rationale for Study	TMA is a common complication in the stem cell transplant population. Certain populations within the HSCT population are at a higher risk than others. Defibrotide is an endothelial stabilizing agent which may prevent the endothelial damage that triggers TMA in HSCT patients. The feasibility, safety, and efficacy of defibrotide prophylaxis in a pediatric transplant population is unknown.
Primary Objective	To determine the feasibility and safety of defibrotide in children receiving HSCT.
Secondary Objectives	To determine the efficacy of defibrotide prophylaxis in preventing severe TMA in pediatric patients receiving HSCT.
Study Design	Single arm non-randomized Phase II safety and feasibility trial of un-blinded defibrotide prophylaxis.
Number of patients	25
Duration of Therapy	Patients may continue treatment for 28-35 days from time of study drug initiation.
Duration of Follow up	Follow up for 6 months post-HSCT per HSCT standard of care.
Duration of study	The study will reach completion 30 months from the time the study opens to accrual.
Study Drugs	Defibrotide 6.25mg/kg IV Q6h for 28-35 days.
Safety Assessments	Weekly inpatient assessments of administration feasibility, hypersensitivity reaction, and bleeding while defibrotide is administered. This includes all HSCT SOC evaluations including routine clinical evaluations and laboratory assessments.
Efficacy Assessments	Efficacy will be based on overall incidence of TMA as well as incidence of severe TMA within 6 months post-HSCT, as defined in the protocol.

Unique Aspects of this Study	This is the first study to evaluate safety and efficacy of defibrotide in pediatric patients for prevention of severe TMA.
------------------------------	--

List of Abbreviations

AE	adverse event
ALP	alkaline phosphatase

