1.3 Rationale for the Proposed Study

Upon retrospective review of our cases of TMA and the medical literature, we are now classifying patients as either standard-risk for the development of TMA, or high-risk, based on the following clinical criteria:

1. Patients undergoing tandem autologous transplant with thiotepa in one or more of the conditioning regimens.

OR:

2. Patients with at least 3 of the following characteristics:
 - a) >10 years of age
 - b) Non-Caucasian race/ Hispanic ethnicity
 - c) Undergoing haploidentical transplant
 - d) Minor ABO Mismatch

Using these criteria, we retrospectively reviewed 160 transplants performed from 1/1/13 to 9/30/16. There were 13 cases of TMA total (8.1%), with 7 cases (4.4%) deemed severe by the onset of renal failure, development of pericardial effusion, and/or death. In the 138 standard-risk patients, there were 6 total cases of TMA, but only 1 was severe (0.7%). Conversely, in the 22 high-risk patients there were 7 total TMA cases, 6 of which were severe (27.3%). Most cases showed evidence of evolving TMA before Day +100 post-HCT, and some cases of TMA were evident within a week following HCT.

Several groups have demonstrated that the onset of endothelial injury and clinical TMA typically begins within 4-6 weeks following HCT (Jodele Blood Rev 2015, Obut BMT 2016). Therefore, the hypothesis is that in high-risk patients the administration of certain combinations of high-dose conditioning agents (radiation and/or chemotherapy) and/or post-HSCT inflammatory events initiate the complement pathway to aberrantly attack the endothelium. Although the current standard treatment for post-transplant microangiopathic processes involves targeting inflammatory mediators with complement blockade and plasmapheresis, these therapies do not address the prevention or treatment of the initial pathologic trigger, namely, endothelial damage.

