2.2 Secondary

- To determine if administration of prophylactic Defibrotide will prevent the development of TMA in clinically high-risk patients compared to historic controls.
 - Incidence of TMA in the first 6 months post-HSCT will be compared to incidence in a similar cohort of historical controls.
 - Incidence of severe TMA as defined by any TMA with the following complications:
 - Renal dysfunction requiring dialysis
 - Pleural or pericardial effusion requiring any medical or surgical intervention
 - CNS dysfunction including seizure, PRES
 - Death

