2.4.2 Secondary Endpoints

- Incidence of TMA as diagnosed by criteria listed in section 7.2.1.
- Incidence of severe TMA as diagnosed by criteria listed in 7.2.2.

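### Severe TMA is defined in three different ways: the endpoint in 7.2.2 drops death and adds admission over 90 days, while the 6/22 benchmark counts death and is not to be re-scored

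*Combined protocol and SAP*

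**What the plan says.** The protocol describes severe TMA in three places.

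- **Objective (2.2).** "Incidence of severe TMA as defined by any TMA with the following complications": dialysis; pleural or pericardial effusion requiring intervention; CNS dysfunction including seizure and PRES; death.
- **Endpoint (2.4.2 and 7.2.2).** The endpoint is "Incidence of severe TMA as diagnosed by criteria listed in 7.2.2". Section 7.2.2 reads "Any TMA meeting criteria described in 7.2.1 with any of the following additional features". It lists dialysis, effusion requiring intervention and CNS dysfunction including seizure, and then adds "Inpatient admission > 90 days duration directly related to TMA management". Death is not listed.
- **Benchmark (1.3).** The historical cases were "deemed severe by the onset of renal failure, development of pericardial effusion, and/or death". Of 22 high-risk patients, 7 had TMA and 6 of those were severe (27.3%).

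The abstract sets the trial window as "incidence of severe TMA within 6 months post-HSCT, as defined in the protocol". For TMA overall, 2.2 says "Incidence of TMA in the first 6 months post-HSCT will be compared to incidence in a similar cohort of historical controls". Section 1.3 gives no follow-up window for the historical cases.

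Section 8.1 states power for severe TMA against 6/22, and 8.2.1 uses 28%. Section 8.4.3 plans the comparison with historical controls without giving a count. Section 8.1 also has the study re-evaluated if one patient develops severe TMA; that rule does not say which definition applies.

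**The concern.** A comparison with historical controls is interpretable only if the same event is counted in both groups over the same period. Here, a patient with TMA who dies without any other 7.2.2 feature is severe under the objective and under the benchmark, but not under the endpoint. A patient with TMA and a long TMA-related admission as the only feature is severe under the endpoint alone. Because 8.1 carries 6/22 forward as a fixed figure and nothing provides for re-scoring, the plan as written sets a 7.2.2 count against a count made on other criteria.

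At stake is the reading of the severe-TMA result, including which way a borderline result falls. If 7.2.2 also governs the one-case rule in 8.1, a TMA death with no other feature would not trigger that rule. It would still count toward the rules for TMA overall in 8.1 (2 patients) and 7.1 (more than 2).

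**Working it through.** **Definitions side by side**

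| Feature | Objective 2.2 | Endpoint 7.2.2 | Benchmark 1.3 |
|---|---|---|---|
| Kidney | dialysis | dialysis | renal failure |
| Effusion | pleural or pericardial, with intervention | pleural or pericardial, with intervention | pericardial |
| CNS | seizure, PRES | seizure named; wording open, so PRES may fit | not listed |
| Death | yes | **no** | yes |
| Admission > 90 days | no | **yes** | no |
| Window | 6 months | 6 months (abstract) | not stated |

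The 7.2.2 list is narrower than the benchmark on death, and on its wording also on kidney (dialysis) and on pericardial effusion (intervention). It is wider on pleural effusion, CNS and admission. The net direction cannot be read from the text.

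**Reproducing the plan's power**

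Inputs from 8.2.1: historical rate 28%, trial rate 4%, alpha 5%, N=24.

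- One-sample exact binomial: reject if X ≤ 2, since P(X ≤ 2 | 24, 0.28) = 0.0196 and P(X ≤ 3) = 0.064. Power = P(X ≤ 2 | 24, 0.04) = 0.3754 + 0.3754 + 0.1799 = 0.931.
- One-sample normal approximation, two-sided: 93.4%.

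Both are close to the stated 92%. The 70% in 8.1 is approached by a different test: a one-sided two-sample z test, 6/22 against 4% in 24, gives 71.6%. So the arithmetic in 8.2.1 is not the difficulty here; the definition behind the historical rate is.

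**Sensitivity to re-scoring**

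The documents do not say which criterion made each of the 6 cases severe, so the re-scored count k of 22 is an assumption, shown as a range. Its ceiling is 7 unless TMA itself is re-diagnosed, because only 7 of the 22 had TMA. The trial rate is held at 4% with N=24. The plan names no test, so two are shown.

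(a) One-sample exact, one-sided 5%: c is the largest value with P(X ≤ c | 24, k/22) ≤ 0.05; power = P(X ≤ c | 24, 0.04).

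(b) Two-sample Fisher exact, two-sided 5%: power by full enumeration, with the control count binomial(22, k/22) and rejection counted only when the trial rate is lower. The p-values take the control count as k.

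| Benchmark | (a) c | (a) size | (a) power | (b) power | p at 0/24 | p at 1/24 |
|---|---|---|---|---|---|---|
| 7/22 | 3 | 0.028 | 98.6% | 72.4% | 0.003 | 0.020 |
| 6/22 | 2 | 0.023 | 93.1% | 60.0% | 0.008 | 0.043 |
| 5/22 | 1 | 0.017 | 75.1% | 45.5% | 0.019 | 0.090 |
| 4/22 | 0 | 0.008 | 37.5% | 30.1% | 0.045 | 0.178 |

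The drop in (a) at 4/22 is partly discreteness: P(X ≤ 1) there is 0.051, just over the limit.

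**Effect of one uncounted trial death**

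Keep the benchmark at 6/22. If two trial patients are severe under 2.2 and one of them qualifies by death alone, 2/24 (Fisher p = 0.128) becomes 1/24 (p = 0.043) under 7.2.2.

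**The case against.** The strongest reply is that no effect is shown. Nothing in 1.3 says that any of the 6 high-risk cases was severe by death alone; if none was, and the renal and effusion cases also meet 7.2.2, re-scoring leaves 6/22. The 5/22 and 4/22 rows are assumptions, and holding the trial rate at 4% while the definition moves is a simplification. Treating the historical count as random also smooths the Fisher gradient: with the count fixed at its value, Fisher power is 75.1%, 75.1%, 37.5% and 37.5% for 7, 6, 5 and 4 of 22. All of this stands, and it means the size is a sensitivity range and not an estimate. With the count fixed, though, the loss from 6/22 to 5/22 is larger.

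Section 8.4.3 also says the complications will be compared, which could bring in death, and 8.4.4 reports non-relapse mortality. Deaths would therefore not vanish from the report. Neither provision puts them into the severe-TMA count that 8.1 powers.

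On the window, 2.2 can be read as intending the same 6 months for the controls, and 1.3 says most cases were evolving before Day +100. That makes the window the weaker part of the concern. The one-case rule only prompts re-evaluation, and enrolment may continue. Finally, this is a secondary endpoint of a safety and feasibility pilot, which limits the weight of the point but does not resolve a conflict between two definitions of the same endpoint.

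**Conclusion.** The concern holds and should be fixed. The objective and the endpoint disagree on whether death makes TMA severe, the benchmark rests on a third set of criteria, and nothing provides for re-scoring. Moving one historical case is enough to take an observed 1/24 from p = 0.043 to p = 0.090, and to lower one-sample exact power from 93.1% to 75.1%. An observed 0/24 would remain below 0.05 across the whole range examined, so the conclusion is not always sensitive. The direction of any bias is unknown. These sizes rest on assumed re-scored counts, a 4% trial rate, N=24 and tests that the plan does not name.

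**What to change.** 1. Reconcile 2.2 and 7.2.2 into one definition that includes death, as 2.2 already does. State which deaths count, for example any death after a TMA diagnosis, or only deaths attributed to TMA.
2. Before analysis, re-score the 22 historical high-risk patients under that definition over the same 6-month window. Then restate the benchmark and the power in 8.1 and 8.2.1, naming the test.
3. State in 8.1 that the one-case rule uses the same definition.
4. If the historical charts cannot support re-scoring, report severe TMA descriptively, without a test against 27.3%.
5. As a clarification, state in 8.2.2 that a patient who dies after a TMA diagnosis stays in the analysis with that outcome, consistent with 8.4.1.

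The cost is wording changes in 2.2, 7.2.2, 8.1, 8.2.1 and 8.2.2 and a re-read of 22 charts. The documents do not say whether those charts hold every item, which is why the descriptive fallback is needed. The restated benchmark and power may be less favourable than the present ones.
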